3C.4.1. Collect Retrospective Activity Data. Data from 1,000 tenured adult *Strava* users in the 4 U.S. Census regions will be obtained. *Eligibility criteria includes: 1+ full calendar year of activities; at least 156 activities [3 per week] in past year; 18 and older; U.S. resident.* Users will consent for their data to be accessed and a full calendar year of all *Strava* data will be procured, including following variables, *which are*

all available through the Strava API⁸⁰: distance, moving time, pace, elapsed time, start time, end time, date, type of activity (e.g., run; ride; *swim*), and gear used. These data will be paired with calendar data (i.e., day of week, season, holidays) and weather data *from National Oceanic and Atmospheric Administration databases* (i.e., temperature; precipitation; humidity; UV level; wind) to create a multivariate time series of data for each user. This data will be subjected to machine learning analytics to develop an algorithm that forecasts the likelihood that the user will engage in outdoor activity *in near future (duration of reliable prediction will be modeled)*, including the nature of exercise bout (e.g., length of time; UV level). We will recruit users by posting in clubs, a popular *Strava* feature (e.g., *Strava* Club has over 662,800 members⁸¹). We will post in various clubs until 1,000 eligible members are enrolled. Participants will receive an authentication screen (see **Figure 1**) that identifies data we will access and how it will be used. We will raffle off 10 \$50 gift cards as an incentive.

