3C.4.2. Use Machine Learning (AI) to Predict Outdoor Activity. Deep learning analytics, a branch of machine learning that mimics structures of the human brain, are innovative techniques that give more flexibility and are typically more accurate than autoregressive integrated moving average (ARIMA) models.^{82,83} To predict future outdoor activity, we will use a type of artificial neural network, Recurrent Neural Network (RNN), well-suited to temporal prediction,⁸⁴ along with a Long Short-Term Memory (LSTM) approach.⁸⁵ LSTM neural network can learn long-term patterns and dependencies and provide stability to prediction algorithm by evaluating when it is advantageous to remember or forget previous state, making assessing typically intractable problems with very complex data possible. LSTM has been applied to several temporal processing problems in public health, including influenza,⁸⁶ colorectal cancer,⁸⁷ and fall prevention.⁸⁸ We will build a machine learning model using Keras and TensorFlow in R. First, we will split time-series data into a training set and a validation set of users, in an 80/20 split. We will train a LSTM neural network on the training set. Once trained, we will layer on auxiliary calendar and weather data to try to reduce the model's error and maximize predictive power. We will compare models using several fit indices: Mean Absolute Percentage Error, Root Mean Squared Error, and Root Mean Squared Percentage Error, and plot predicted scores across each model with observed scores to determine closest match. We will apply the model with best fit and most accurate prediction to time-series in validation set to assess how well it predicts new data.

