3C.4.3. Integrate Predicted Outdoor Activity with Sun Protection Advice. Algorithms from our *sunZapp* mobile app⁷¹ (see **Box 2**) will be employed to tailor sun safety advice to predicted outdoor physical activity *and personal risk* of *Strava* users. *Machine learning model will predict users' risk of UV-exposure (i.e., timing and duration of outdoor exercise). Users' personal risk (i.e., skin type: hair and eye color and skin tanability⁸⁹) will be collected in SS user profile when first accepted by Strava users. We will use 5-day Planner in sunZapp to combine predicted time and duration of outdoor activity bout, forecast UV Index, and personal risk to calculate Strava users' time to sunburn and provide tailored sun safety advice, based on the World Health Organization's (WHO) Global UV Index guidelines.⁹⁰ To be modified based on results from focus groups.* we plan to deliver the advice in the evening and morning before the predicted outdoor physical activity bout (and during extended bouts) through *Strava* comments and emails (see **3C.5**). *Because Strava users get notified by email and in the app, they likely will see the message before their next outdoor activity.*

Box 2: Prior Research on Sun Safety Advice Algorithms

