database that delivers tailored, evidence-based sun safety emails/comments through the *Strava* interface based on predicted outside physical activity, forecast UV, and *personal skin cancer risk*. SS development will follow KB's standard iterative production. We will develop goals and behavioral objectives and outline of messages based on focus group results, theoretical models (see **3A.3**), GSS social media messages (see **Box 3**), and *sunZapp*'s advice algorithms (see **Box 2**). KB media developers will produce a database with the *Strava* API and algorithm predicting future outdoor physical activity (see **3C.4**) to power the SS interface and schedule sun safety messages (when and to whom). The SS database will determine time of day, date, location (from Wi-Fi, cellular network, or GPS), and forecast UV, and use *sunZapp* algorithm and outdoor physical activity algorithm to provide emails/activity comments over *Strava* platform advising precaution when UV Index is forecast to be ≥ 3 during predicted outdoor activity time (i.e., risk is moderate, high, or extreme based on Global UV Index standards⁹⁰). Messages will be sent at various times, based on outdoor activity algorithm (see **3C.4.2**); tentatively, we plan to deliver advice on the evening before outdoor activity bout to promote planning for sun safety (e.g., forecast UV Index for time outdoors; packing sunscreen and selecting hats, sunglasses, and protective clothing), just before predicted time of exercising, and during extended exercise (e.g., reapply sunscreen; use shade). We will ask focus groups about timing preferences (see **3C.3**). *Strava* users are accustomed to receiving emails/comments and most check them regularly (see **Box 1**). SS messages will be available through any device. Users will not need to interact with a separate app/interface. A specifications document with technical requirements, database plans, flow charts, and content outline will be developed.

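### The prediction model is validated on same-period data with no rule limiting weather inputs to what is known at message time, so the validation does not measure accuracy in use

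*Combined protocol and SAP*

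**What the plan says.** All references are to the combined protocol and SAP.

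**Development data (3C.4.1).** One full year of past activity is to be obtained from 1,000 users and joined to calendar variables and to weather "from National Oceanic and Atmospheric Administration databases". The weather variables are listed as follows: "i.e., temperature; precipitation; humidity; UV level; wind) to create a multivariate time series of data for each user". The section does not say whether these are observations or archived forecasts, or how they are lagged against the bout. The horizon is left open: "duration of reliable prediction will be modeled". UV level appears in this section both as an input and as part of what is to be forecast.

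**Model building and validation (3C.4.2).** The division is by person: "we will split time-series data into a training set and a validation set of users, in an 80/20 split". After the LSTM is trained, "we will layer on auxiliary calendar and weather data to try to reduce the model's error and maximize predictive power". The best-fitting model is then applied "to time-series in validation set to assess how well it predicts new data".

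**Use.** Under 3C.4.3 the sunZapp planner is to "combine predicted time and duration of outdoor activity bout, forecast UV Index, and personal risk", and advice goes out the evening and the morning before the predicted bout. Section 3C.5 says "tentatively, we plan to deliver advice on the evening before outdoor activity bout", adds messages just before and during long sessions, and triggers advice on a forecast UV Index of at least 3.

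**The concern.** A model that schedules messages should be tested with the information it will hold when it schedules them, and on dates later than those it learned from. The stated validation requires neither.

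The first gap is in the inputs. If the temperature, rain, humidity, wind and UV that occurred on the day of a bout are supplied to predict that bout, the model sees values that do not exist the evening before. For UV it would also receive part of its own target.

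The second gap is in time and does not depend on how the weather wording is read. The split is by user only, so new data means new people and not later dates.

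The validation result is the main quantitative evidence for Aim 2, and the model decides when messages are sent and to whom. If that result does not carry over, pilot messages will be sent for bouts that do not happen, or missed for bouts that do, at a rate nobody has estimated.

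**Working it through.** The plan states no accuracy target, horizon, forecast error or weather effect, so there is no figure to reproduce. The check has three parts.

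**1. Development and use side by side**

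| | Development and validation | Use in the pilot |
|---|---|---|
| Weather and UV | NOAA values for the past year; product and lag not stated (3C.4.1) | Forecast UV (3C.4.3, 3C.5); other weather inputs not stated |
| Moment of prediction | Not stated | Evening or morning before, or just before the bout |
| Dates | Past year, model built in Months 6-8 (3C.1) | Months 16-21 (3C.1) |
| People | 80/20 split of 1,000: 800 to train, 200 to validate | Recruited separately (3C.6) |

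The people row is tested by the user split. The weather and timing rows are not specified on the development side. The dates row is never tested: every pilot prediction falls at least seven full months (Months 9-15) after the model is built.

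**2. Share of the weather gain that carries over (illustrative algebra)**

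Let W be observed weather and F its forecast, both standardised, with correlation r. The documents give no r, so it is assumed.

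*Activity follows actual weather:* Y = bW + e.
- Error reduction seen in validation on W: b².
- Fitted on W, run on F: the added error is b²·Var(W − F) = b²(2 − 2r), so the reduction is b² − b²(2 − 2r) = b²(2r − 1).
- Fitted and run on F: b²r².

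| r | Fitted on W, run on F (2r − 1) | Fitted and run on F (r²) |
|---|---|---|
| 0.9 | 80% | 81% |
| 0.7 | 40% | 49% |
| 0.6 | 20% | 36% |

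*Activity follows the forecast:* Y = cF + e.
- The coefficient fitted on W is cr, and validation on W shows a reduction of c²r².
- Run on F, the reduction is c² − c²(1 − r)² = c²r(2 − r).
- The ratio of use to validation is (2 − r)/r: 1.1/0.9 = 1.22 at r = 0.9 and 1.3/0.7 = 1.86 at r = 0.7. Here validation understates.

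These are shares of the gain from the weather layer, not of total accuracy.

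**3. Effect on overall discrimination (simulation, all inputs assumed)**

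Daily activity follows a logistic model with intercept −0.3, a habit effect of 1.0 per SD and a weather effect of 0 to 1.0 per SD. There are 400,000 records, half for training and half for testing. The model is trained on observed weather, then tested on observed weather (validation) and on forecasts (use). Entries are validation AUC minus in-use AUC at forecast correlations of 0.95 / 0.85 / 0.70.

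| Weather effect per SD | Activity follows actual weather | Activity follows forecast |
|---|---|---|
| 0 | 0.000 / 0.000 / 0.000 | 0.000 / 0.000 / 0.000 |
| 0.25 | 0.001 / 0.003 / 0.005 | −0.001 / −0.002 / −0.003 |
| 0.5 | 0.002 / 0.008 / 0.017 | −0.003 / −0.007 / −0.012 |
| 1.0 | 0.008 / 0.025 / 0.049 | −0.008 / −0.022 / −0.040 |

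The gap is nil without a weather effect, small for modest effects, and changes sign with what people respond to. The simulation covers the weather inputs only. It does not price the untested shift to later dates.

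**The case against.** The strongest reply is that the plan never says same-day observed weather predicts the same-day bout. A recurrent network that forecasts the next bout can be built on values up to the prediction time only, and the text does not exclude that. Box 2 names a NOAA UV product that is itself a forecast. This stands as far as it goes: observed same-date weather is an inference. It is still the natural reading, because weather is listed beside day of week, season and holidays with no lag. The Box 2 product belongs to sunZapp and covers UV only. The sunZapp planner, for its part, takes the predicted bout as an input, so its use of forecast UV does not show what weather the LSTM receives.

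The user split is sensible, since pilot participants are recruited separately. That stands, and the split should be kept. It answers a different question from whether the model works on later dates.

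There are later checks. The usability test (3C.5.3) asks 30 users over four weeks about prediction accuracy, and the Study Procedures text schedules a Month 15 review of the algorithm's validity. The first is prospective but small and self-reported, with no metric stated. The second names no data. Nor does modelling the reliable horizon help if it is done with hindsight weather.

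Message timing is tentative and includes messages close to the bout, when weather is nearly known. That would shrink the gap for those messages but not for the evening ones.

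A reader might infer two stronger things. One is that validation necessarily overstates accuracy. The documents do not support this, because the sign depends on which inputs are used and on whether users follow actual or forecast weather. The other is that 20-80% of the model's accuracy would vanish. That range is 1 − (2r − 1) for r from 0.9 to 0.6, all assumed, and applies only to an unknown gain from the weather layer.

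**Conclusion.** The gap is real and worth closing before the model is built. As written, the validation does not restrict inputs to those available at message time and never tests later dates, so it is not a measure of in-use accuracy.

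It may misstate that accuracy in either direction. Overstatement needs three conditions together: target-day observed weather as input, a weather effect that the model retains, and activity that follows actual rather than forecast weather. The documents settle none of the three. Under assumed inputs the AUC difference runs from −0.040 to +0.049, and is within 0.017 either way for weather effects up to 0.5 per SD.

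The pilot's primary analysis, a paired t-test of sun protection before and after, is unaffected. What is at stake is the accuracy claim for Aim 2 and the quality of message scheduling that rests on it.

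**What to change.** In 3C.4.1 and 3C.4.2:

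1. State the NOAA product and the lag. For each predicted bout, admit only weather and UV values available at the planned message time: archived forecasts at that lead or, where archives are lacking, the last observed values before that time.
2. Train, select and validate on those inputs. If messages are planned at more than one lead, report accuracy for each.
3. Keep the 80/20 user split. Report Aim 2 accuracy for the 200 held-out users in forward (rolling-origin) week blocks spread over the year and including high-UV months, with each block predicted by a model trained only on earlier dates.
4. Refit the final model on all data afterwards.

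A single hold-out of the last eight weeks is simpler (8/52 = 15% of the year) but worse. If the year runs January to December, it removes a low-UV season from training and reports accuracy largely outside the high-UV period that 3C.4 targets.

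The cost is extra data preparation, several model fits instead of one, and a reported accuracy that may be somewhat lower. With one year per user, no forward block has seen its own season before, so the estimate will tend to be cautious about seasonal patterns; the report should say so. No new participants are needed.

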Online and mobile technologies for tracking physical activity have exploded over the past decade. Many Americans wear activity trackers or GPS-enabled devices (e.g., Fitbit and Garmin) and upload their physical activity data to websites/mobile apps. Strava, an activity tracking app and social networking site for athletes of all abilities, is one of the most popular. Millions share their own activities and follow and comment on physical activity by other users in their network. This R21 research responds to PAR-19-309 "Stimulating Innovations in Behavioral Intervention Research for Cancer Prevention and Control" with the goal of increasing skin cancer prevention among a high-risk population, adults who engage in outdoor physical activity by establishing **feasibility** of interfacing sun protection advice with the *Strava* website/mobile app. Specifically, we will show that we can create an algorithm that a) predicts when individuals are likely to be engaged in physical activity outdoors and b) delivers sun safety advice tailored to time, location, and personal risk (e.g., skin sun sensitivity). We need to establish feasibility before conducting a future randomized trial evaluating the efficacy of this unique intervention. The *Strava Sun* (SS) program will obtain user data and deliver ecologically-valid sun safety advice by utilizing *Strava*'s open-source Applications Programming Interface (API) and location-based advice algorithms developed earlier for a sun safety mobile app, *sunZapp*, funded by the NCI.¹⁷ Sun safety messages provided through SS will also be derived from sun safety messages from our *Go Sun Smart* (GSS) program for individuals engaged in outdoor recreation.¹⁸ Both the algorithms from *sunZapp* and the GSS messages improved sun safety practices of adults in general and while on vacation in randomized trials (see **Boxes 1 and 2**) and provide the **scientific premise** for developing SS. Based on the Extended Parallel Processing Model¹⁹ of persuasive communication, Diffusion of Innovation Theory²⁰ (DIT), and Social Cognitive Theory (SCT),²¹ we hypothesize that SS will increase sun protection by elevating perceived risk, self-efficacy, and response efficacy and promoting prevention skills acquisition.²¹ The specific aims are to:

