1. Gather formative data from focus groups of outdoor exercisers, both *Strava* users and non-users, on interest in receiving personalized, location-based sun protection advice and willingness to use sun protection advice sent through the *Strava* mobile app before and during physical activity.
2. Develop a machine learning algorithm to predict future time of day and duration of outdoor physical activity from activities logged on *Strava* through its API from users who consent to data access.
3. Modify the algorithms in *sunZapp* and social media messages from GSS to create a prototype of the SS intervention that delivers location-based, tailored sun safety advice to *Strava* users through *Strava* comments, which can be accessed through the *Strava* website and mobile app, and emails.
4. Test with *Strava* users the acceptability of the SS prototype and sun safety messages, ways of interacting

with it, and barriers/willingness to allowing access.

The R21 research is significant and innovative. A sun protection interface for the Strava platform will allow us to identify a large population of Americans at high risk for skin cancer who routinely engage in physical activity, often outdoors with high-risk sun exposure, and reach them with sun safety advice they may not seek on their own to motivate them to practice sun safety during outdoor activities. Dissemination of evidence-based sun safety messages through this widely-used “social network for athletes” is innovative. It will help to meet the goals set by both NCI and the U.S. Surgeon General to prevent skin cancer among physically-active Americans to reverse the one cancer currently increased by physical activity.

The project will be led by Principal Investigators, [name] and [name] at Klein Buendel, Inc. (KB). *Co-Investigators at Colorado State U., [name] (project statistician) and [name] (machine learning expert) will create the predictive algorithms, assisted by a machine learning graduate student.* [name], *project consultant*, at U. of Connecticut will provide expertise on physical activity promotion and interventions delivered via social media. [name], recent software engineer at *Strava, will also serve as a project consultant* and advise on delivering the sun protection intervention through *Strava*. Media developers at KB will produce the API database and program.

3A. SIGNIFICANCE

3A.1. The Skin Cancer Problem

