Our team has collected formative data relevant to the proposal. [name] surveyed 278 adults who engaged in moderate-intensity physical activity. Physically-active participants had more sun exposure, higher perceived skin cancer risk, but similar sun protection as inactive adults. There were 4 types of active participants: 1) low perceived risk, no tanning interest, and high frequency of exercise in peak UV (17%); 2) low perceived risk, no tanning interest, and avoid exercise during peak UV (36%); 3) high perceived risk, no tanning interest, and avoid exercise during peak UV (18%); 4) high perceived risk, high tanning interest, and exercise during peak UV (29%). A second online survey assessed members of a large workout group (n=60; 91% non-Hispanic, 86% White, 67% female) in Denver in 2018. 94% exercised outdoors for ≥ 30 minutes at least 3 times per week (51% 5 times/week). 53% did so between 8:00am and 7:00pm and 16%, 10:00am and 4:00pm when UV is highest. 93% used a device to track physical activity, with a GPS-enabled watch most common (48%). 82% uploaded their activities on a tracking site (61% used *Strava*). Of *Strava* users, 78% regularly or always uploaded their activity; 43% uploaded 2-4 times per week, and 41% ≥ 5 times per week; 51% checked *Strava* notifications regularly. 73% were somewhat (51%) or very (22%) willing to get sun safety messages on *Strava*; 89% were somewhat (54%) or very (35%) willing to download an app that connects with *Strava* and uses their data to provide sun safety advice. Respondents, on average, received 2.6 sunburns in the past year (range: 0-20), with 2.5 of these sunburns occurring while exercising outdoors (range: 0-15).

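### Section 3C.4.2 scores no simple benchmark beside the LSTM, so its held-out error cannot show whether the model adds predictive value over a habit rule

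*Combined protocol and SAP*

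**What the plan says.** Aim 2 (2. Specific Aims) is to "Develop a machine learning algorithm to predict future time of day and duration of outdoor physical activity". The same section says the project will show that it can create an algorithm that "predicts when individuals are likely to be engaged in physical activity outdoors". Section 3C.4 states the working premise: what a user did before, and in what circumstances, forecasts what the user does next.

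Section 3C.4.2 sets out the modelling. Deep learning is preferred because it is "typically more accurate than autoregressive integrated moving average (ARIMA) models", with two references. The data are split 80/20 by user. The steps are then:

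- One LSTM is fitted to the training users.
- Calendar and weather variables are added to that network, in the hope of lowering its error.
- For the choice between the resulting versions, the text says: "We will compare models using several fit indices: Mean Absolute Percentage Error, Root Mean Squared Error, and Root Mean Squared Percentage Error". Predictions from each version are also plotted against what was observed.
- The version judged best is applied to the validation users.

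Two later steps touch on accuracy. Section 3C.5.3 asks 30 usability testers by phone how accurate the predictions were. Under Study Procedures, the investigators and a consultant review the algorithm's validity in Month 15, before the pilot starts in Month 16. The Statistical Analysis Plan section does not mention the algorithm.

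**The concern.** The only models described are the LSTM without and with auxiliary data. No persistence rule, same-weekday rule, user average or ARIMA model is scored, and no minimum accuracy is set. An error of a given size on the 200 held-out users could reflect a network that has learned something useful. It could equally be what any rule that repeats the user's habits would achieve.

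This matters because the predictions decide when messages go out (3C.4.3 and 3C.5), and because the Month 15 review has neither a comparator nor a criterion. The review could pass a complex model that does no better than a one-line rule, and nobody would know.

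**Working it through.** The documents give no accuracy, power or sample-size figure for Aim 2, so there is no figure to reproduce. The check is mainly a reading of the text, supported by simple arithmetic.

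**1. Inputs from the documents.** 1,000 users and at least 156 activities in the past year (3C.4.1); 80/20 split by user (3C.4.2). So 0.20 × 1,000 = 200 validation users, and 156/52 = 3.0 activities per week at the minimum.

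**2. Search for a comparator.** None is named in 2. Specific Aims, 3C.1 to 3C.4.3, 3C.5.3, the description of the usability participants, Study Procedures or the Statistical Analysis Plan. The phrase "We will compare models using several fit indices" does not exclude other models, but the only ones described are LSTM versions. Section 3C.4.2 does specify software, architecture, split ratio and three error measures, so the method is otherwise given in some detail.

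**3. What no skill looks like, by day.** Assumption: at most one session per day. For a user active on k of 7 days, a constant yes/no rule is right on max(k, 7−k)/7 of days. A constant forecast of p = k/7 has RMSE √(p(1−p)).

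- k = 3: accuracy 4/7 = 57%.
- k = 5: accuracy 5/7 = 71%; RMSE √(5/7 × 2/7) = 0.45.
- k = 6: accuracy 6/7 = 86%.

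At the eligibility minimum, 156/365 = 42.7% of days are active, so always predicting no activity is right on 57.3%.

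**4. What no skill looks like, by hour.** Time of day is part of the plan's target. Assumption: five one-hour sessions a week. Then 5/168 = 3% of hours are active, always predicting no is right in 97% of hours, and the constant-forecast RMSE is √(0.03 × 0.97) = 0.17. The no-skill level thus depends heavily on resolution and on the user, and an error figure cannot be read without it.

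**5. A usual-weekday rule.** Assumption: k usual days a week, each kept with probability h, and the weekly total held at k. Activity on other days then has probability q = k(1−h)/(7−k), and the rule is right on [kh + (7−k)(1−q)]/7 of days.

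| k | h | q | accuracy |
|---|---|---|---|
| 3 | 0.70 | 0.225 | 74% |
| 3 | 0.90 | 0.075 | 91% |
| 5 | 0.70 | 0.750 | 57% |
| 5 | 0.90 | 0.250 | 86% |

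Over k = 3 to 5 and h = 0.70 to 0.90, the range is about 57% to 91%. The lowest value is a limiting case, because there the usual days are less likely to be active than the others (0.70 against 0.75). The benchmark may be weak or strong, and the documents do not settle which.

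**6. Can 200 users support the comparison?** For a paired per-user difference in error, two-sided 0.05, normal approximation: (1.960 + 0.842)/√200 = 0.20 SD at 80% power, and (1.960 + 1.282)/√200 = 0.23 SD at 90%. The SD of that difference is not given in the documents, so the result stays in SD units.

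**The case against.** The strongest reply is that Aim 2 is a development and feasibility aim. It promises no superiority over a simpler rule, and the ARIMA remark is a cited, general reason for choosing a method. That stands: this is a missing benchmark, not a contradiction or a failed claim. It is also fair that the plan does assess performance, through plots against observed scores, validation in new users, tester interviews and the Month 15 review. None of these supplies a comparator. The LSTM before auxiliary data is an internal reference, but it shows only what calendar and weather data add.

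Three stronger readings are tempting and are not supported:

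- A reader might infer that a habit rule must already predict well because users are selected for regularity. The criterion of 156 activities a year is one of volume. It requires no fixed weekday or hour.
- A reader might infer from Box 1, where 51% exercised outdoors 5 times a week, that accuracy near 70% would mean no skill for about half the users. That figure comes from 60 members of one Denver workout group and counts times, not days. Among the Strava users, 41% uploaded at least 5 times a week. Percent correct by day is also neither a planned measure nor the planned target, and only 16% exercised between 10:00am and 4:00pm, when UV is highest.
- A reader might infer that the pilot's result is at risk. Its primary analysis is the pre-to-post change in sun protection (3C.7) and does not use the model's skill.

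**Conclusion.** The gap is real and cheap to close. Followed as written, section 3C.4.2 will yield the absolute error of the selected LSTM in 200 new users. It cannot say whether the LSTM improves on the habit premise in section 3C.4, and the general advantage over ARIMA stays cited but unchecked in these data. The no-skill level is not trivial: 57% to 71% of days right for users active 3 to 5 days in 7, with RMSE 0.45 at 5 in 7, assuming at most one session per day. These figures illustrate the problem on a daily yes/no scale. They do not estimate benchmark performance on time of day and duration, which the documents do not allow. The consequence is confined to what Aim 2 and the Month 15 review can conclude.

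**What to change.** In 3C.4.2, add at least one habit benchmark: each user's weekday-by-hour frequency over recent weeks, or a repeat of the same slot last week. Compute it only from data before each forecast time. Score it on the same 200 validation users, with the same measures and targets as the LSTM. Report the LSTM's improvement over it with a confidence interval obtained by resampling users, and put that result before the Month 15 review ahead of the pilot. ARIMA is an optional further comparator, since the text invokes it. The decision on which model to deploy can remain with the review; an automatic rule is not needed.

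The cost is one paragraph and a little more analysis on data already held, with no new participants. The downside is that the reported performance may look less impressive.
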